Urinalysis ⁴	X					
Pregnancy test ⁵	X	X			X	
Safety/Disease Assessments						
Tumor Assessments ⁶				X		
Adverse Event Assessments ⁷		X	X	X	X	X
Concomitant Medication ⁸		X	X	X	X	X
Study Treatment						
Dacomitinib		As per dosing regimen in original protocol				

- Informed Consent:** All patients must sign an informed consent document prior to any study-related procedures that are not considered to be standard of care and prior to receiving study drug.
- Hematology:** Be performed according to local standard clinical practice. The interval for laboratory assessments should not be longer than every 8 weeks.
- Blood Chemistry:** Be performed according to local standard clinical practice. The interval for laboratory assessments should not be longer than every 8 weeks.
- Urinalysis:** Be performed according to local standard clinical practice.
- Pregnancy Test:** Pregnancy Test (serum or urine) for women of child-bearing potential shall be done at screening and before investigational product administration at the baseline visit. It should be repeated the end of study treatment, and additionally whenever one menstrual cycle is missed, or when potential pregnancy is otherwise suspected. Additional pregnancy tests may also be undertaken if requested by institutional review boards (IRBs)/ethics committees (ECs), or if required by local regulations.
- Tumor Assessments:** On-study tumor assessments should be performed according to site standard-of-care imaging modality. The interval for monitoring disease status and for progression of disease should not be longer than every 6 months.
- Adverse Event Assessment:** Following the first dose, adverse events (AEs) and serious adverse events (SAEs) should be assessed and documented during the study reporting period. All reported study drug-related adverse events must be followed until the event has resolved, returned to baseline, or has been deemed irreversible, or until death, whichever occurs first.
- Concomitant Medications:** Review medications taken by the patient since the last visit to determine whether or not treatment with dacomitinib is contraindicated.

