5.9.1. CYP2D6 Substrates

The use of drugs that are highly dependent on CYP2D6 for metabolism requires consideration of both the therapeutic index and the degree of CYP2D6 metabolism. Substitution within the therapeutic class is recommended if possible, otherwise the directions below should be followed.

- Drugs dependent on CYP2D6 metabolism with narrow therapeutic index are prohibited: eg, procainamide, pimozide and thioridazine.
- Administration of drugs which are highly dependent on CYP2D6 metabolism: dose reduction should be based on substrate sensitivity to CYP2D6 metabolism. As a guidance, a starting dose reduction of 75% (25% of the dose given without co-administration with dacomitinib) and close clinical monitoring is required.
- For drugs that are partly dependent on CYP2D6-mediated metabolism, there is a high likelihood of supra-therapeutic exposure in combination with dacomitinib. No dose reduction is required when starting dacomitinib but clinical monitoring is required and, based on patient response, dose-reduction may be necessary.

- Pro-drugs, or drugs with highly active metabolites such as codeine and tramadol should be replaced by an alternative within the therapeutic class as conversion to the pharmacologically active moiety is CYP2D6 metabolism-dependent and their exposure with the co-administration of dacomitinib may be sub-therapeutic. Opiates such as morphine, hydromorphone, oxycodone and oxycodone can be used as substitutes to replace codeine or tramadol for analgesia.

[Appendix 2](#) provides a comprehensive list of CYP2D6 substrates coded according to the therapeutic index and the degree of CYP2D6 metabolism. This is not an all-inclusive list. If there is uncertainty whether a concomitant medication is contraindicated, the Investigator should contact the Sponsor study team.

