Grade 2 Localized intervention indicated; or oral intervention indicated (eg, antibiotic, antifungal, antiviral); or nail fold edema or erythema with pain; or associated with discharge or nail plate separation; or limiting instrumental ADL	Topical antibiotics and vinegar soaks* Apply silver nitrate weekly
Grade 3 Surgical intervention, or IV antibiotics indicated; or limiting self-care ADL	Topical antibiotics and vinegar soaks* Apply silver nitrate weekly Surgical consultation as needed
*Topical antibiotics/ vinegar soaks	Topical antibiotics: Clindamycin 1%, erythromycin 1% Vinegar soaks consist of soaking fingers or toes in a 1:1 solution of white vinegar in water for 15 minutes every day ± For a video on how to apply silver nitrate, visit: http://www.youtube.com/watch?v=HF5oopqheJY

Pruritis/Itching guidelines:

Prophylaxis against dry skin would include:

- Initiation of skin moisturizing regimen prior to first dose. Non-scented emollient skin cream should be used;
- Avoidance of excessive exposure to hot water during showering/ bathing;
- Avoidance of household tasks involving immersion in hot water/ detergent/ solvents;

- Avoidance of excessive sun exposure/ tanning. Use sunscreen containing zinc oxide or titanium dioxide with SPF at least 30: apply every two hours when sun exposure is anticipated.

	Pruritis Management Guideline
Grade 1: Mild or localized; or topical intervention indicated	Topical steroid moderate/low strength (as listed above for acneiform rash) or Topical antipruritics (pramoxine 1%, doxepin 5% cream) applied twice daily
Grade 2 Intense or widespread, intermittent; skin changes from scratching (eg, edema, papulation, excoriations, lichenification, oozing/crusts); or oral intervention indicated; or limiting instrumental ADL	Topical steroid moderate strength or Topical antipruritics (pramoxine 1%, doxepin 5% cream) applied twice daily AND Oral antihistamines
Grade 3: Intense or widespread, constant; or limiting self care ADL or sleep; or oral corticosteroid or immunosuppressive therapy indicated	Oral antihistamines AND GABA agonists (gabapentin or pregabalin) or Doxepin
	Antihistamines: diphenhydramine 25-50 mg tid; hydroxyzine 25 mg tid; fexofenadine 60 mg tid GABA agonists (adjust if renal impairment) : Gabapentin 300 mg every 8 hours or Pregabalin 50-75 mg every 8 hours Tricyclics: Doxepin 25-50 mg every 8 hours

MUCOSITIS

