S	clomipramine	Tricyclics and Tetracyclics	S	pactimibe	Other Antilipemics
S	clozapine	Antipsychotics	S	paroxetine	Serotonin Reuptake Inhibitors (SSRIs)
PD	codeine	Opioids	S	perhexiline	Vasodilators
S	debrisoquine	Other Antihypertensives	HS	perphenazine	Antipsychotics
HS	desipramine	Tricyclics and Tetracyclics	S	phenformin	Biguanides
S	dexfenfluramine	Anorexics	P	pimozide	Antipsychotics
HS	dextromethorphan	Antitussives	HS	prajmaline	Antiarrhythmics
S	dihydrocodeine	Opioids	P	procainamide	Antiarrhythmics
S	donepezil	Anticholinesterase Inhibitors	S	propafenone	Antiarrhythmics
HS	doxepin	Tricyclics and Tetracyclics	S	propranolol	Alpha/Beta Adrenergic Antagonists
S	duloxetine	Ser-Nor Reuptake Inhibitors (SNRIs)	S	ranolazine	Cardiovascular Drugs
S	encainide	Antiarrhythmics	S	repinotan	Serotonin Receptor Agonist
S	fesoterodine	Muscarinic Antagonists	S	risperidone	Antipsychotics
S	flecainide	Antiarrhythmics	S	ritonavir	Protease Inhibitors
S	fluoxetine	Serotonin Reuptake Inhibitors (SSRIs)	S	sabeluzole	CNS Agents
S	fluphenazine	Antipsychotics	S	sparteine	Antiarrhythmics
HS	fluvoxamine	Serotonin Reuptake Inhibitors (SSRIs)	PD	tamoxifen	Antineoplastic Hormonal
S	gefitinib	Kinase Inhibitors	S	tamsulosin	Alpha/Beta Adrenergic Antagonists
S	haloperidol	Antipsychotics	HS	tetrabenazine	CNS Agents
PD	hydrocodone	Opioids	P	thioridazine	Antipsychotics
S	iloperidone	Antipsychotics	S	timolol	Alpha/Beta Adrenergic Antagonists
S	imipramine	Tricyclics and Tetracyclics	HS	tolterodine	Muscarinic Antagonists
S	lasofoxifene	Estrogen Receptor Modulators	PD	tramadol	Other Analgesics
PD	loratadine	H-1 Receptor Antagonists	HS	traxoprodil	Neuroprotectors
S	maprotiline	Tricyclics and Tetracyclics	S	trazodone	Serotonin Modulators
S	methadone	Opioids	S	trimipramine	Tricyclics and Tetracyclics
S	methamphetamine (MA)	Recreational Drugs	HS	tropisetron	Serotonin HT3 Receptor Antagonists
S	3,4-methylenedioxy-MA	Recreational Drugs	S	venlafaxine	Ser-Nor Reuptake Inhibitors (SNRIs)
HS	methoxyphenamine	Beta Adrenoreceptor Agonist	HS	vernakalant	Antiarrhythmics
S	Methylphenidate	Psychostimulants	S	zuclopenthixol	Antipsychotics
S	Metoclopramide	Other Antiemetics			
HS	High likelihood of supratherapeutic exposure in combination with dacomitinib; dose-reduction and clinical monitoring IS required, if co-administration cannot be avoided: starting dose when coadministration with dacomitinib: 25% of original dose		P	Narrow therapeutic Index : Prohibited in combination with dacomitinib	

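### The Grade 3 pruritus guidance in Appendix 1 prints a doxepin dose without the CYP2D6 conditions that Appendix 2 sets for doxepin

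*Protocol*

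**What the plan says.** The Pruritis Management Guideline in Appendix 1 pairs oral antihistamines at Grade 3 with "GABA agonists (gabapentin or pregabalin) or Doxepin". The dose cell under the table lists doxepin as a tricyclic: "Doxepin 25-50 mg every 8 hours". For gabapentin and pregabalin the same cell prints a caution to adjust in renal impairment. It prints no caution for doxepin.

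Appendix 2 lists doxepin with code HS. The legend for that code warns of likely supratherapeutic exposure and continues: "dose-reduction and clinical monitoring IS required, if co-administration cannot be avoided". It then fixes the dose: "starting dose when coadministration with dacomitinib: 25% of original dose".

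Section 5.9.1 covers drugs highly dependent on CYP2D6 in the same sense: "a starting dose reduction of 75% (25% of the dose given without co-administration with dacomitinib) and close clinical monitoring is required". That sentence opens by calling the figure guidance, and it follows a statement that the reduction should depend on how sensitive the substrate is.

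At Grades 1 and 2 the table also offers "Topical antipruritics (pramoxine 1%, doxepin 5% cream) applied twice daily". That is topical use and is outside this point.

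**The concern.** Section 5.6 presents Appendix 1 as the specific guidance for common EGFR-inhibitor toxicities and says its own general advice does not replace it. Sites are therefore likely to prescribe from the table. A clinician who takes the doxepin dose from the Grade 3 row would miss the protocol's own interaction rule for a drug it flags as likely to reach supratherapeutic levels. Because the adjacent drugs do carry a dose caution, its absence for doxepin can be read as meaning that none is needed.

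What is at stake is the safety of individual patients. No endpoint, analysis population or summary depends on it.

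**Working it through.** The protocol gives no statistical figure to reproduce here. The check compares the two appendices and adds a short dose calculation.

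**Conditions side by side**

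| HS condition (Appendix 2) | Grade 3 pruritus row (Appendix 1) |
|---|---|
| Avoid co-administration where possible | Absent; doxepin is joined to the alternatives by a plain *or* |
| Start at 25% of the original dose | Absent; 25 to 50 mg every 8 hours, with nothing marking it as reduced |
| Clinical monitoring | Absent |
| Reference to Appendix 2 or Section 5.9.1 | Absent |

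**Route.** The row does not print one. A milligram dose every 8 hours under the tricyclics, listed separately from the 5% cream, is read as systemic.

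**Dose.** Every 8 hours is three doses a day.

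- Printed: 25 × 3 = 75 mg/day and 50 × 3 = 150 mg/day.
- HS start, assuming the printed dose is the ordinary unreduced one: 25 × 0.25 = 6.25 mg and 50 × 0.25 = 12.5 mg per dose.
- Per day: 6.25 × 3 = 18.75 mg and 12.5 × 3 = 37.5 mg.
- Ratio: 75 / 18.75 = 150 / 37.5 = 4.

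**Is doxepin avoidable in this row?** The dose cell names six drugs: diphenhydramine, hydroxyzine, fexofenadine, gabapentin, pregabalin and doxepin. Only doxepin is in Appendix 2. Gabapentin and pregabalin, the alternatives to it, are not listed there.

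**Is it isolated?** Appendix 2 lists 16 HS + 57 S + 5 PD + 3 P = 81 drugs. Appendix 1 offers 29 named medicines, counting the components of combination products separately and leaving out chlorhexidine (to be avoided) and sunscreen ingredients. Doxepin is the only one found in both lists. The count covers named drugs only; the mucositis text also allows unnamed systemic analgesics.

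**When could the two drugs overlap?** Section 5.5 interrupts dacomitinib for Grade 3 toxicity and allows it to resume at Grade 2 or lower, or at baseline, possibly at the same dose level. The pruritus table has no study-treatment line, unlike the diarrhea and keratoconjunctivitis tables, and nothing tells the site to stop or reduce doxepin when dacomitinib restarts. The exposure at issue is therefore residual dacomitinib during the interruption, and doxepin continued after resumption.

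**The case against.** The strongest reply is that this is a missing cross-reference and not a contradiction. HS is not a ban. A site can satisfy both parts by choosing gabapentin or pregabalin, or by reducing doxepin. Section 5.9.1 applies to every CYP2D6 substrate, the introduction to Appendix 2 asks investigators to check interactions for all concomitant medication, and nothing in Appendix 1 waives either. This stands as a limit on severity. It does not make the printed dose consistent with the HS rule.

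Other safeguards help less. Section 5.9.1 says "If there is uncertainty whether a concomitant medication is contraindicated, the Investigator should contact the Sponsor study team", but a dose printed by the sponsor gives little cause for uncertainty. The Schedule of Activities footnote says "Review medications taken by the patient since the last visit to determine whether or not treatment with dacomitinib is contraindicated"; that review may come after doxepin has started, and it asks about dacomitinib rather than the doxepin dose. Inclusion criterion 2 keeps out patients with an ongoing Grade 3 or intolerable Grade 2 dacomitinib-related event at entry, but not those with a later onset.

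A second reply is that the 75% reduction is softer than it looks, being introduced as guidance in Section 5.9.1 and in the text of Appendix 2. That is right for those two places, but the HS legend carries no such qualifier. It is also fair that Section 5.9.1 recommends substitution within the therapeutic class, and the GABA agonists are not tricyclics. That doxepin is avoidable here is an inference from the HS legend and the alternatives in the row.

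Third, the Grade 2 row offers only topical treatment and oral antihistamines, so a site managing by current grade would not be directed to systemic doxepin once dacomitinib may resume. This narrows the overlap. It does not close it, because no instruction says to stop doxepin.

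**Conclusion.** The inconsistency holds and is minor. The Grade 3 pruritus row offers systemic doxepin at a stated dose without any of the three conditions that Appendix 2 attaches to it, although two alternatives in the same row are free of that listing.

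The factor of 4 compares doses and does not measure exposure or harm. It rests on the printed dose being unreduced. If that assumption fails, the factor falls away, but the avoid-where-possible and monitoring conditions are still missing. Calling the use systemic is a reading of the dose line.

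Frequency cannot be estimated. The protocol gives no rate of Grade 3 pruritus or of doxepin use, and no duration of residual dacomitinib exposure in patients. The problem is confined to one drug in one row and is expected to arise seldom.

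**What to change.** Either of two changes would resolve it; the sponsor's clinical pharmacology group should choose.

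1. Delete systemic doxepin from the Grade 3 pruritus row, together with its tricyclic dose line. Gabapentin and pregabalin remain.
2. Keep it only as a fallback when gabapentin and pregabalin are unsuitable. State the HS-reduced starting dose, require clinical monitoring, refer to Appendix 2, and say that the same conditions apply when dacomitinib is resumed.

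The cost is a wording change to one appendix row and its dose line. Endpoint, population and analysis are unaffected.

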Appendix 2. Guidance on Concomitant Medications involved in CYP2D6 Pathway

For CYP2D6 substrates, drugs for which substitution, dose modification and/or monitoring is advised are listed below along with the narrow therapeutic index drugs that are substrate of CYP2D6 and its administration is prohibited. This listing **is not an all-inclusive list, and** will be monitored by Sponsor study team for required updates (addition, deletion) but in all instances investigators should review potential for drug-drug interaction for concomitant medications and take appropriate measures of substitution or dose modification.

- For administration of drugs which are highly dependent on CYP2D6 metabolism:
 - Dose reduction should be based on substrate sensitivity to CYP2D6 metabolism. As a guidance a starting dose reduction of 75% (25% of the dose given without coadministration with dacomitinib) and close clinical monitoring is required.
- For the drugs that are partly dependent on CYP2D6-mediated metabolism, there is a high likelihood of supra-therapeutic exposure in combination with dacomitinib; **clinical** monitoring is required and dose-reduction may be necessary.
- Pro-drugs, or drugs with highly active metabolites such as codeine and tramadol should be replaced by an alternative within the therapeutic class as conversion to the pharmacologically active moiety is CYP2D6 metabolism-dependent and their exposure with the co-administration of dacomitinib may be subtherapeutic. Opiates such as morphine, hydromorphone, oxymorphone and oxycodone can be used as substitutes to replace codeine or tramadol for analgesia.

CODE	DRUG	THERAPEUTIC CLASS	CODE	DRUG	THERAPEUTIC CLASS
S	amiflamine	Monoamine Oxidase Inhibitors (MAOIs)	HS	metoprolol	Alpha/Beta Adrenergic Antagonists
HS	amitriptyline	Tricyclics and Tetracyclics	S	mexiletine	Antiarrhythmics
S	aripiprazole	Antipsychotics	S	mianserin	Tricyclics and Tetracyclics
HS	atomoxetine	Psychostimulants	S	mirtazapine	Tricyclics and Tetracyclics
S	brofaromine	Monoamine Oxidase Inhibitors (MAOIs)	HS	nebivolol	Alpha/Beta Adrenergic Antagonists
S	bufuralol	Alpha/Beta Adrenergic Antagonists	S	nefazodone	Serotonin Modulators
S	carvedilol	Alpha/Beta Adrenergic Antagonists	S	nicergoline	Vasodilators
S	chlorpheniramine	H-1 Receptor Antagonists	S	nortriptyline	Tricyclics and Tetracyclics
S	chlorpromazine	Antipsychotics	S	(S)-ondansetron	Serotonin HT3 Receptor Antagonists
S	citalopram	Serotonin Reuptake Inhibitors (SSRIs)	S	oxycodone	Opioids
S	clomipramine	Tricyclics and Tetracyclics	S	pactimibe	Other Antilipemics
S	clozapine	Antipsychotics	S	paroxetine	Serotonin Reuptake Inhibitors (SSRIs)
PD	codeine	Opioids	S	perhexiline	Vasodilators
S	debrisoquine	Other Antihypertensives	HS	perphenazine	Antipsychotics
HS	desipramine	Tricyclics and Tetracyclics	S	phenformin	Biguanides
S	dexfenfluramine	Anorexics	P	pimozide	Antipsychotics
HS	dextromethorphan	Antitussives	HS	prajmaline	Antiarrhythmics
S	dihydrocodeine	Opioids	P	procainamide	Antiarrhythmics
S	donepezil	Anticholinesterase Inhibitors	S	propafenone	Antiarrhythmics
HS	doxepin	Tricyclics and Tetracyclics	S	propranolol	Alpha/Beta Adrenergic Antagonists
S	duloxetine	Ser-Nor Reuptake Inhibitors (SNRIs)	S	ranolazine	Cardiovascular Drugs
S	encainide	Antiarrhythmics	S	repinotan	Serotonin Receptor Agonist
S	fesoterodine	Muscarinic Antagonists	S	risperidone	Antipsychotics
S	flecainide	Antiarrhythmics	S	ritonavir	Protease Inhibitors
S	fluoxetine	Serotonin Reuptake Inhibitors (SSRIs)	S	sabeluzole	CNS Agents
S	fluphenazine	Antipsychotics	S	sparteine	Antiarrhythmics
HS	fluvoxamine	Serotonin Reuptake Inhibitors (SSRIs)	PD	tamoxifen	Antineoplastic Hormonal
S	gefitinib	Kinase Inhibitors	S	tamsulosin	Alpha/Beta Adrenergic Antagonists
S	haloperidol	Antipsychotics	HS	tetrabenazine	CNS Agents
PD	hydrocodone	Opioids	P	thioridazine	Antipsychotics
S	iloperidone	Antipsychotics	S	timolol	Alpha/Beta Adrenergic Antagonists
S	imipramine	Tricyclics and Tetracyclics	HS	tolterodine	Muscarinic Antagonists
S	lasofoxifene	Estrogen Receptor Modulators	PD	tramadol	Other Analgesics
PD	loratadine	H-1 Receptor Antagonists	HS	traxoprodil	Neuroprotectors
S	maprotiline	Tricyclics and Tetracyclics	S	trazodone	Serotonin Modulators
S	methadone	Opioids	S	trimipramine	Tricyclics and Tetracyclics
S	methamphetamine (MA)	Recreational Drugs	HS	tropisetron	Serotonin HT3 Receptor Antagonists
S	3,4-methylenedioxy-MA	Recreational Drugs	S	venlafaxine	Ser-Nor Reuptake Inhibitors (SNRIs)
HS	methoxyphenamine	Beta Adrenoreceptor Agonist	HS	vernakalant	Antiarrhythmics
S	Methylphenidate	Psychostimulants	S	zuclopenthixol	Antipsychotics
S	Metoclopramide	Other Antiemetics			
HS	High likelihood of supratherapeutic exposure in combination with dacomitinib; dose-reduction and clinical monitoring IS required, if co-administration cannot be avoided: starting dose when coadministration with dacomitinib: 25% of original dose		P	Narrow therapeutic Index : Prohibited in combination with dacomitinib	
PD	pro-drug: active ingredient ONLY or partially upon CYP2D6 metabolism. High likelihood of subtherapeutic exposure in combination with dacomitinib		S	High likelihood of supratherapeutic exposure in combination with dacomitinib; clinical monitoring is required and dose-reduction may be necessary	

9/5/2012 v1.0 . Pfizer Inc.
